#### **Statistical Analysis**

Details of statistical analysis of anticipated events, including the frequency of review and threshold to trigger an aggregate analysis of anticipated events will be provided in a separate Anticipated Events Safety Monitoring Plan (ASMP).

#### Attachment 10: Patient-Reported Outcomes Questionnaires

# European Organization for Research and Treatment of Cancer Quality of Life Questionnaire-Core 30 (EORTC-QLQ-C30)

# EORTC QLQ-C30 (version 3)

We are interested in some things about you and your health. Please answer all of the questions yourself by circling the number that best applies to you. There are no "right" or "wrong" answers. The information that you provide will remain strictly confidential.

Please fill in your initials:        Your birthdate (Day, Month, Year):        Today's date (Day, Month, Year):     31											
		Not at All	A Little	Quite a Bit	Very Much						
1.	Bo you have any trouble doing strenuous activities, like carrying a neavy shopping bag or a suitcase?	1	2	3	4						
2.	Do you have any trouble taking a long walk?	1	2	3	4						
3.	Do you have any trouble taking a short walk outside of the house?	1	2	3	4						
4.	Do you need to stay in bed or a chair during the day?	1	2	3	4						
5.	Do you need help with eating, dressing, washing yourself or using the toilet?	1	2	3	4						
Dı	uring the past week:	Not at All	A Little	Quite a Bit	Very Much						
6.	Were you limited in doing either your work or other daily activities?	) 1	2	3	4						
7.	Were you limited in pursuing your hobbies or other leisure time activities?	1	2	3	4						
8.	Were you short of breath?	1	2)	3	4						
9.	Have you had pain?	Ì	2	3	4						
10.	Did you need to rest?		2	3)	4						
11.	Have you had trouble sleeping?	1	2	3	4						
12.	Have you felt weak?	1 🗸	2	3	4						
13.	Have you lacked appetite?	1	2	3	4						
14.	Have you felt nauseated?	1	2	3	4						
15.	Have you vomited?	1	2	3	4						
16.	Have you been constipated?	1	2	3	4						
	Please go on to the next nage										

Please go on to the next page

During the past week:	Not at All	A Little	Quite a Bit	Very Much				
17. Have you had diarrhea?	1	2	3	4				
18. Were you tired?	1	2	3	4				
19. Did pain interfere with your daily activities?	1	2	3	4				
20. Have you had difficulty in concentrating on things, like reading a newspaper or watching television?	1	2	3	4				
21. Did you/feel tense?	1	2	3	4				
22. Diel you worry?	1	2	3	4				
23. Did you feel irritable?	1	2	3	4				
24. Did you feel depressed?	1	2	3	4				
25. Have you had difficulty remembering things?	1	2	3	4				
26. Has your physical condition or medical treatment interfered with your family life?	1	2	3	4				
27. Has your physical condition or medical treatment interfered with your social activities?	1	2	3	4				
28. Has your physical condition or medical treatment caused you financial difficulties?	1	2	3	4				
For the following questions please circle the number between 1 and 7 that best applies to you								

29. How would you rate your overall health during the past week? 1 2 3 4 5 6 Very poor Excellent 30. How would you rate your overall quality of life during the past week? 7 1 2 3 4 5 6 Very poor Excellent

© Copyright 1995 EORTC Quality of Life Group. All rights reserved. Version 3.0

## European Quality of Life 5 Dimensions Questionnaire (EQ-5D-5L)

**Health Questionnaire** 

English version for the UK

UK (English) © 2009 EuroQol Group EQ-5D™ is a trade mark of the EuroQol Group

Under each heading, please tick the ONE box that best describ	es your health TOD
MOBILITY	
I have no problems in walking about	
I have slight problems in walking about	
I have moderate problems in walking about	
I have severe problems in walking about	
I am unable to walk about	
SELF-CARE	
I have no problems washing or dressing myself	
I have slight problems washing or dressing myself	
I have moderate problems washing or dressing myself	
I have severe problems washing or dressing myself	
I am unable to wash or dress myself	
USUAL ACTIVITIES (e.g. work, study, housework, family or leisure activities)	
I have no problems doing my usual activities	
I have slight problems doing my usual activities	
I have moderate problems doing my usual activities	
I have severe problems doing my usual activities	
I am unable to do my usual activities	
PAIN / DISCOMFORT	
I have no pain or discomfort	
I have slight pain or discomfort	
I have moderate pain or discomfort	
I have severe pain or discomfort	
I have extreme pain or discomfort	
ANXIETY / DEPRESSION	
I am not anxious or depressed	
I am slightly anxious or depressed	
I am moderately anxious or depressed	
I am severely anxious or depressed	
I am extremely anxious or depressed	

2

UK (English) © 2009 EuroQol Group EQ-5D™ is a trade mark of the EuroQol Group

		The best health you can imagine
We would like	e to know how good or bad your health is TODAY.	100
• This scale is r	numbered from 0 to 100.	 
	ne best health you can imagine.	90
0 means the v	worst health you can imagine.	
Mark an X on	the scale to indicate how your health is TODAY.	
	write the number you marked on the scale in the box	
below.		– 70
		55
	YOUR HEALTH TODAY =	50
		45
		40
		± 35
		30
		= 25
		20
		15
		 
		± 5
		o
		The worst health you can imagine

3

UK (English) © 2009 EuroQol Group EQ-5D™ is a trade mark of the EuroQol Group

#### Attachment 11: Daratumumab Monotherapy Period For Subjects No Longer Receiving JNJ-63723283 In Combination With Daratumumab

#### **Overall Design for Daratumumab Monotherapy Period**

Each cycle is 28 days, and administration of daratumumab is to occur weekly for Cycles 1 and 2, every other week for Cycles 3 to 6, and every 4 weeks for Cycles 7 and onwards until disease progression, pregnancy, unacceptable toxicity, loss of follow-up, withdrawal of consent, or death. Scheduled assessments to be performed during the Daratumumab Monotherapy Period for Subjects No Longer Receiving JNJ-63723283 in Combination with Daratumumab are outlined in the Time and Events Schedule in Table 24.

# Table 24: Time and Events Schedule – Daratumumab Monotherapy Period for Subjects No Longer Receiving JNJ-63723283 in Combination with Daratumumab

		Cycles	s 1 and	2	Cycle	s 3 to 6	Cycles 7+	EOT a	
Study Day	1	8	15	22	1	15	1	Post-Treatment Week 4 (±7 days)	
Procedures/Assessments Study procedures									
Informed consent	Subj	ects m	ust sign	the info				-specific procedures are performed.	
Physical Examination		-	-		Symp	tom-direct	ted physical exai	nination only	
Dosing									
Daratumumab 16 mg/kg dosing (IV)	Х	Х	Х	Х	Х	Х	Х		
Preinfusion and postinfusion medications b	Х	Х	Х	Х	Х	Х	Х		
Weight	Х				Х		Х	Х	
Vital Signs (immediately before start and at end of each daratumumab infusion)	Х	Х	Х	X	Х	X	Х	Х	
Laboratory Assessments c									
Urine or serum pregnancy test (women of childbearing potential only)				•		Only if	f clinically indica	ated.	
Biochemistry	Х				Х		Х	Х	
Hematology	Х	Х	Х	Х	Х	Х	Х	Х	
Investigator assessment of response c		•	•	.			• •		
SPEP and 24-hour UPEP d , Serum calcium corrected for albumin d , Serum FLC & serum/urine immunofixation d , Bone marrow aspirate/bone marrow biopsy Skeletal survey/Assessment of lytic bone disease	As	s clinic						standard of care until PD maging (X-ray, CT, or MRI may be used)	
Assess extramedullary plasmacytomas						As per	local standard of	care	
Ongoing Subject Review						1.5 per			
SAEs, including SPMs	Continuous from time of ICF until EOT Visit or until the subject withdraws consent for study participation or until the subject starts subsequent anticancer therapy e whichever occurs first. Beyond the EOT Visit reporting period after the last dose of study medication, information on SAEs, including SPMs, considered possibly, probably or definitely related to study drug will continue to be collected.								

- a) To occur 4 weeks (±7 days) after the last dose of study drug or as soon as possible before the start of subsequent therapy.
   b) Refer to Section 6.4.1.2 and Section 6.4.1.3 for additional information.
- c) Evaluations will be conducted at the local laboratory and responses will be interpreted by the investigator.
- d) Disease assessments SPEP, UPEP, and serum calcium corrected for albumin should be collected at an interval consistent with the investigator's standard of care. For guidance, the Sponsor recommends (but does not require) local laboratory assessments to be conducted every cycle for the first 18 months after initiating daratumumab monotherapy, and every other month thereafter.
- e) For subjects who have received additional treatment with therapeutic intent for multiple myeloma during the SAE reporting period, only SAEs that are considered to be possibly, probably, or definitely related to daratumumab must be reported (unless the subject has been withdrawn from the study).

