## End of Study

Subjects will discontinue the study upon completion of the End of Treatment Visit.

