## 12.3. Procedures

#### 12.3.1. All Adverse Events

All adverse events and special reporting situations will be reported from the time a signed and dated ICF is obtained until 30 days after the last dose of study drug, or until start of subsequent anticancer therapy or the subject withdraws consent for study participation, if earlier, which may include contact for follow-up of safety. For subjects who have received subsequent treatment with therapeutic intent for multiple myeloma during the adverse event reporting period, only adverse events that are considered to be possibly, probably, or definitely related to JNJ-63723283 or daratumumab need to be reported. Serious adverse events, including those spontaneously reported to the investigator, must be reported using the Serious Adverse Event Form. Serious adverse events considered by the investigator to be related to JNJ-63723283 or daratumumab should continue to be reported during the follow-up period. The Sponsor will evaluate any safety information that is spontaneously reported by an investigator beyond the time frame specified in the protocol.

Disease progression should not be recorded as an adverse event or serious adverse event term; instead, clinical sequelae resulting from disease progression/lack of efficacy will be reported if they fulfill the serious adverse event definition (refer to Section 12.1.1). Death should not be recorded as an adverse event or serious adverse event, but as the outcome of an adverse event. The adverse event that resulted in the death should be reported as a serious adverse event. All events that meet the definition of a serious adverse event will be reported as serious adverse events, regardless of whether they are protocol-specific assessments. Anticipated events will be recorded and reported as described in Attachment 9.

All adverse events, regardless of seriousness, severity, or presumed relationship to study drug, must be recorded using medical terminology in the source document and the CRF. Whenever possible, diagnoses should be given when signs and symptoms are due to a common etiology (eg, cough, runny nose, sneezing, sore throat, and head congestion should be reported as "upper respiratory infection"). Investigators must record in the CRF their opinion concerning the relationship of the adverse event to study therapy. All measures required for adverse event management must be recorded in the source document and reported according to Sponsor instructions.

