# 12.3.1.1. Daratumumab Monotherapy Period

Non-serious adverse events will not be reported during the daratumumab monotherapy period. However, SAEs (including SPMs) must be reported continuously from time of ICF until EOT Visit or until the subject withdraws consent for study participation or until the subject starts subsequent anticancer therapy whichever occurs first. Beyond the EOT Visit reporting period after the last dose of study medication, information on SAEs, including SPMs, considered possibly, probably or definitely related to study drug will continue to be collected.

Serious Adverse Event reporting after the final database lock, established once Protocol Amendment 2 is implemented at all sites, will be limited to SAE reporting into the Sponsor's global safety database, using SAE Form (paper form) faxed to Sponsor's Local Operational Company/Local Safety Officer.

SAEs (see Section 12.3.2) should include information on study agent administration and concomitant medications associated with an SAE.

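### Table 24 footnote e limits SAE reporting after a switch of therapy to daratumumab-related events in subjects who had JNJ-63723283, contradicting Table 1 and Section 12.3.1

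*Protocol*

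**What the plan says.** Protocol Attachment 11 governs follow-up once combination dosing has stopped. Its schedule, Table 24, is titled for the "Daratumumab Monotherapy Period for Subjects No Longer Receiving JNJ-63723283 in Combination with Daratumumab".

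The SAE row of Table 24 asks for every SAE, second primary malignancies (SPMs) included, from consent until the earliest of three events: the EOT Visit, withdrawal of consent, or the start of new anticancer therapy. For the time after EOT it says that "SAEs, including SPMs, considered possibly, probably or definitely related to study drug will continue to be collected". Section 12.3.1.1 ends in the same way ("considered possibly, probably or definitely related to study drug will continue to be collected"), as does the monotherapy paragraph of Section 9.1.4.

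Footnote e is attached to the new-therapy stop in that row. Its trigger is "For subjects who have received additional treatment with therapeutic intent for multiple myeloma during the SAE reporting period" and its rule is "only SAEs that are considered to be possibly, probably, or definitely related to daratumumab must be reported". It then adds an exemption: "unless the subject has been withdrawn from the study".

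For the same situation outside the monotherapy period, Section 12.3.1 says that "only adverse events that are considered to be possibly, probably, or definitely related to JNJ-63723283 or daratumumab need to be reported", and Table 1 gives the same rule. Section 12.3.1 adds that SAEs attributed to either drug remain reportable in follow-up.

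On leaving the study in the monotherapy period, Section 10.1.1 says "Subjects will discontinue the study upon completion of the End of Treatment Visit". Separately, it requires withdrawal of a subject with an SPM that surgery alone cannot treat.

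**The concern.** Footnote e is the only SAE rule in the protocol that expressly drops JNJ-63723283, and it does so in the table used for people who have received that drug. A site that follows Table 24 literally could leave out an SAE it attributes to JNJ-63723283 alone. Attachment 9 lists pneumonitis, colitis, hepatitis, nephritis and endocrinopathies as anticipated from that drug's mechanism, so the omitted category is not an empty one.

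No second data stream would catch the omission. In this period non-serious events are not reported (Section 12.3.1.1), nothing is entered in the eCRF once Amendment 2 is implemented at a site (Section 17.5), and monitoring is confined to SAEs that have already been reported (Section 17.8). The combination was stopped because of a changed benefit/risk balance in a related combination study (Section 1.4). That makes an inconsistent attribution rule for the stopped drug harder to justify.

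**Working it through.** There is no figure in the plan to reproduce. The check is a comparison of the SAE rules and a timeline.

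**1. Rules that apply after new therapy starts**
- Table 1: events related to JNJ-63723283 or daratumumab.
- Section 12.3.1: the same two drugs.
- Table 24 footnote e: daratumumab only.

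**2. Rules on related SAEs in later follow-up**
- Section 12.3.1: SAEs related to either drug.
- Section 9.1.4 (monotherapy paragraph), Section 12.3.1.1 and the Table 24 SAE row: SAEs related to *study drug*, with neither agent named.

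**3. Timeline for a combination-exposed subject who stops daratumumab and starts new therapy before EOT**
- Up to the start of new therapy, all SAEs are reportable.
- From the start of new therapy to EOT, the all-SAE duty has ended (Section 12.3.1.1 and the Table 24 row). The *study drug* sentence has not yet begun, because it covers only the time after EOT. Footnote e is the one rule specific to the monotherapy period, and it names daratumumab only.
- After EOT, the *study drug* sentence applies.

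**4. Length of the middle interval**

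Footnote a sets EOT at 4 weeks ± 7 days after the last dose, that is 28 − 7 = 21 to 28 + 7 = 35 days, or as soon as possible before new therapy. If EOT is done before new therapy, the interval is zero. If new therapy starts soon after the last dose and EOT is held at the end of its window, the interval approaches 35 days. This assumes EOT takes place on schedule; a late or missed EOT would lengthen it.

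**5. Meaning of *study drug***

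Sections 7 and 11.1 use the term for both agents, and Attachment 11 does not redefine it. In Table 24, however, daratumumab is the only drug dosed, and footnote a uses *study drug* for the last dose given, which in this period is daratumumab. Next to footnote e, a site could reasonably carry that narrower sense into the SAE row.

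**6. The exemption**

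Section 10.1.1 withdraws a subject whose SPM surgery alone cannot treat. If that subject has also received new myeloma therapy, footnote e lifts the duty to report. The SAE row above it, and Sections 9.1.4 and 12.3.1.1, say that related SAEs including SPMs are still collected. These statements cannot both be followed.

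**7. Where the effect lands**

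SAP Section 1 places the analysis after the database lock that follows implementation of Amendment 2 at all sites. Section 12.3.1.1 sends SAEs after that lock only to the sponsor's global safety database.

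**The case against.** The strongest answer is that other provisions still cover JNJ-63723283. Section 12.3.1 keeps SAEs related to either drug reportable in follow-up. Section 12.3.2 requires all SAEs during the study to be reported within 24 hours. The *study drug* sentences take over after EOT, in a protocol that uses the term for both agents. Footnote a often puts EOT ahead of new therapy. Within the remaining window, the footnote releases only SAEs judged not even possibly related to daratumumab, the drug given most recently.

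This stands as a limit on the size of the problem. A reader might infer from footnote e that late JNJ-63723283-related SAEs need not be reported at all, or that every combination subject who starts new therapy is affected. The provisions above rule out both readings. They do not remove the conflict between the footnote and the parallel rules, and a site in the monotherapy period will work from Table 24.

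A reader might also take the exemption to cover everyone who completes EOT, since subjects then leave the study. The text does not support this. Section 10.1.1 says such subjects discontinue the study, and it lists withdrawal reasons separately, as applying before EOT. The SPM conflict survives, although the malignancy that triggers withdrawal arises before it and is reportable as an SAE while all-SAE reporting is still open.

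Finally, the 5-month precaution after JNJ-63723283 could be taken as the length of the exposed period. It concerns contraception, related reproductive precautions and live vaccines, not safety reporting. Expressing one missed event as a share of the small run-in cohort would be no more than an illustration; it is not an expected effect.

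**Conclusion.** Footnote e is wrong as written. It contradicts Table 1 and Section 12.3.1 on which attributions count after a switch, and it sits badly with the *study drug* wording in its own table row. The practical gap is mainly from the start of new therapy to EOT: nothing when EOT comes first, and up to about 35 days after the last dose when it does not. After EOT the problem is ambiguity, not a stated release from reporting. The withdrawal exemption is a second, smaller contradiction, confined to subjects withdrawn for an SPM.

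The conclusion assumes that sites apply the footnote literally and that EOT takes place within its window. The documents do not say how many combination-exposed subjects went on to monotherapy and then to new therapy, so no event count or rate can be attached. The consequence is a possible omission from the sponsor's safety database. The SAP tables are not affected.

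**What to change.** - In Table 24 footnote e, change *related to daratumumab* to *related to daratumumab or JNJ-63723283*.
- In Section 9.1.4 (monotherapy paragraph), Section 12.3.1.1 and the Table 24 SAE row, replace *study drug* in the related-SAE sentence with the same two names. This makes explicit the sense already used in Sections 7 and 11.1.
- Reconcile the footnote's exemption for withdrawn subjects with the continued collection of related SAEs including SPMs. One way is to limit it to subjects who have withdrawn consent, a stop that Section 12.3.1 and the Table 24 row already use.

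The cost is a wording change to one footnote and three sentences, with possibly a few more SAE forms. No visit, procedure or analysis changes.

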### AMENDMENT HISTORY

The statistical analysis plan (SAP) has been revised and description of the changes and the section affected are provided below.

Amendment -1 (07Sep2018)

Summary of change: 1. Included biomarker analysis

Applicable Section	Description of Change
1.9 Biomarker	Since biomarker analysis would be included in the final CSR, this new section for biomarker analysis was added in this SAP.

## 1. ANALYSIS DETAILS

This document contains definitions of analysis sets, derived variables and planned data presentation specifications which will be used in clinical study report of study 54767414MMY2036. The analysis will be performed after final data base lock when protocol 54767414MMY2036, Amendment 2 is approved and implemented at all sites.

## 1.1. Overview of Study Design

This is a randomized, open-label, multicenter, multiphase study assessing the efficacy and safety of JNJ-63723283 (an anti-PD-1 monoclonal antibody) in combination with daratumumab compared with daratumumab alone in subjects with multiple myeloma who have received at least 3 prior lines of therapy including a PI and an IMiD or whose disease is double refractory to both a PI and an IMiD. A diagram of the study design is provided in Figure 1.

As of 25 May 2018, the Sponsor terminated further enrollment into this study and subjects in Screening were deemed Screen Failures and were not further randomized into the study. Subjects continuing on study will receive daratumumab monotherapy starting 25 May 2018. Part 3 is no longer applicable for this study.

## 1.2. Analysis Sets

- Safety analysis set: includes all subjects who have received at least 1 dose of study agent (JNJ-63723283 or daratumumab, partial or complete) in either Safety Run-in Part 1 or Part 2 of the study. This analysis set will be used for below analyses.
- **Pharmacokinetics (PK)-evaluable analysis set:** includes all subjects who have received at least 1 dose of daratumumab or JNJ-63723283 and have at least 1 post-infusion sample in Safety Run-in Part 1 of the study.
- **Immunogenicity analysis set:** include all subjects who have received at least 1 dose of JNJ-63723283 or daratumumab and have appropriate serum samples for detection of antibodies to JNJ-63723283 or daratumumab (i.e., subjects with at least 1 sample obtained after their first dose of JNJ-63723283 or daratumumab) in Safety Run-in Part 1 of the study.

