
 
To compare the complete response (CR) or better rate and very good partial response (VGPR) or better rate of JNJ-63723283 in combination with daratumumab versus daratumumab alone
 
To compare the duration of response and time to response of JNJ-63723283 in combination with daratumumab versus daratumumab alone
 
To compare the progression-free survival (PFS) and overall survival (OS) of JNJ-63723283 in combination with daratumumab versus daratumumab alone
 
To compare the minimal residual disease (MRD)-negative rate of JNJ-63723283 in combination with daratumumab versus daratumumab alone
 
To evaluate the pharmacokinetic and immunogenicity profile of JNJ-63723283 when given in combination with daratumumab
 
To evaluate the pharmacokinetic and immunogenicity profile of daratumumab when given alone or in combination with JNJ-63723283
 
	
 
CR or better rate, VGPR or better rate, defined as the proportion of subjects with a best response of at least CR or at least VGPR, as defined by the IMWG response criteria
 
Duration of response, defined as the time from onset of first response until date of disease progression or death
 
Time to response, defined as the time between the date of randomization and the onset of first response
 
PFS, defined as the time from the date of randomization to the date of disease progression or death due to any cause, whichever occurs first
 
Overall survival (OS), defined as the time from the date of randomization to the date of death
 
MRD-negative rate, defined as the proportion of MRD- negative subjects
 
Serum JNJ-63723283 pharmacokinetic parameters including but not limited to Cmin and Cmax, and incidence of anti-JNJ-63723283 antibodies
 

Part 3 (Pha	antibodies
	sc 0)

 
Primary
 
To compare progression-free survival (PFS) in subjects treated with JNJ-63723283 in combination with daratumumab versus daratumumab alone
 
	• PFS, defined as the time from the date of randomization to the date of disease progression or death due to any cause, whichever occurs first
Secondary	

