# 9.3.3. Pharmacokinetic Parameters

The PK parameters are defined as:

- $C_{max}$  = Maximum observed concentration
- $C_{min}$  = Minimum observed concentration

For both JNJ-63723283 and daratumumab, the PK evaluations include  $C_{min}$  and  $C_{max}$ . If sufficient data are available, other PK parameters may be calculated. The  $C_{min}$  and  $C_{max}$  will be summarized by descriptive statistical methods for the Safety Run-in, Arm A, and Arm B. If there are sufficient data, then a population PK analysis of serum concentration-time data of daratumumab and JNJ-63723283 may be performed and may include data from other clinical studies. If performed, details will be provided in a population-PK analysis plan and the results of the analysis will be presented in a separate report.

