## 3. COLUMN LAYOUTS FOR TABLES

All tables listed in Section 2 are to be presented with the following columns layout, unless specified otherwise.

Layout 1: To be used in demographics, baseline disease characteristics, prior systemic therapies, medical history, TEAE overview, safety.

Safety Run-in Phase 2		Total
	Arm A	

Layout 2: To be used in exposure tables.

Safety Run-in	Phase 2
	Arm A

Layout 3: To be used in PK tables

Layout 4: To be used in immunogenicity tables

Safety Run-in

Programming notes:

 Footnotes that correspond to the naming of the treatment groups are specified as below: Key: Arm A = daratumumab alone;

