### TSIDEM-ST03: Subject Populations for Evaluation; Safety Analysis Set (Study 54767414MMY2036)

Safety analysis set a	###	###	###	###	####
Pharmacokinetic-evaluable analysis set b Immunogenicity analysis set c	### (xx.x%) ### (xx.x%)				

a Safety analysis set includes all subjects who have received at least 1 dose of study agent (JNJ-63723283 or daratumumab, partial or complete) in either safety run-in or Part 2 of the study.

b Pharmacokinetic-evaluable analysis set includes all subjects who have received at least 1 dose of daratumumab or JNJ-63723283 and have at least 1 postinfusion sample in either safety run-in or Part 2 of the study.

c Immunogenicity analysis set include all subjects who have received at least 1 dose of JNJ-63723283 or daratumumab and have appropriate serum samples for detection of antibodies to JNJ-63723283 or daratumumab (i.e., subjects with at least 1 sample obtained after their first dose of JNJ-63723283 or daratumumab) in either safety run-in or Part 2 of the study

Note: Percentages are calculated with the number of subjects in each group as denominator.

Display Specifications	
Output Identifier	TSIPOP01

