# TPKIR-ST01: Summary of Anti-daratumumab Antibodies Status; Immunogenicity Analysis Set (Study 54767414MMY2036)

—			
Analysis set: immunogenicity	###	###	###
Subjects with appropriate samples a	###	###	###
Subjects with baseline positive samples b,c	### (xx.x%)	### (xx.x%)	### (xx.x%)
Subjects positive for anti-daratumumab antibodies b,d Peak titer	### (xx.x%)	### (xx.x%)	### (xx.x%)
1:20	###	###	###
Subjects positive for neutralizing			
antibodies	### (xx.x%)	### (xx.x%)	### (xx.x%)
Subjects negative for anti-daratumumab antibodies b,e	### (xx.x%)	### (xx.x%)	### (xx.x%)

a Subjects with appropriate samples had 1 or more samples obtained after their first daratumumab administration.

b Denominator is subjects with appropriate samples.

c Subjects with baseline samples positive had samples positive for anti-daratumumab antibodies at baseline, regardless of status after first daratumumab administration.

d Subjects positive for anti-daratumumab antibodies includes all subjects who were positive (treatment-boosted or treatmentinduced) at any time after their first daratumumab administration. Subjects with baseline positive samples and without increased titer after treatment are not considered treatment-boosted.

e Excludes subjects who were positive at any time.

Display Specifications			
Output Identifier	TPKIR01		
Programming notes:			

- 1. Please remove row of "Peak titer" if there is no subject positive for antibodies to daratumumab.
- 2. Please remove 'd' if there are no subject positive for antibody to daratumumab, and change the label 'e' to 'd'.

Display Specifications	
Output Identifier	TPKIR02
Programming notes:	

- 1. Change 'Daratumumab' to 'JNJ-63723283' in the whole table.
- 2. Please remove row of "Peak titer" if there is no subject positive for antibodies to JNJ-63723283.
- 3. Please remove 'd' if there are no subject positive for antibody to JNJ-63723283, and change the label 'e' to 'd'.

				Infusion Related		Toxicity	Daratumumab	Antibody to
Treatment Group	Subject ID	Visit/Time Point CYCLE 1 DAY	Infusion Given?	Reaction	Serious	Grade	Conc. (µg/mL)	Daratumumab Titer
Safety run-in	######	1/PREDOSE CYCLE 2 DAY	Yes	Yes	No	1	LLOQ	NEGTIVE
		1/PREDOSE	No	NA			443.7	1:20

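### SAP 1.2 confines the PK-evaluable and immunogenicity sets to the Part 1 run-in, against the SAP's own population table and, for PK, Protocol 9.3.3

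*SAP*

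**What the plan says.** SAP Section 1.2 defines the safety set over Part 1 or Part 2, but the next two sets more narrowly. PK-evaluable subjects must "have at least 1 post-infusion sample in Safety Run-in Part 1 of the study". The immunogenicity set asks for at least one sample "obtained after their first dose of JNJ-63723283 or daratumumab) in Safety Run-in Part 1 of the study".

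The mock for the population-count table, TSIDEM-ST03 (output TSIPOP01), defines the same two sets differently. Footnote b asks that PK-evaluable subjects "have at least 1 postinfusion sample in either safety run-in or Part 2 of the study". Footnote c, for immunogenicity, asks for a sample "obtained after their first dose of JNJ-63723283 or daratumumab) in either safety run-in or Part 2 of the study".

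Protocol 9.3.3 says that Cmin and Cmax "will be summarized by descriptive statistical methods for the Safety Run-in, Arm A, and Arm B". One of the Part 2 secondary objectives in Protocol 2.1 reads: "To evaluate the pharmacokinetic and immunogenicity profile of daratumumab when given alone or in combination with JNJ-63723283".

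SAP Section 1.8 runs the PK analyses on the PK-evaluable set and the ADA analyses on the immunogenicity set, each by treatment group.

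**The concern.** The SAP gives two incompatible definitions for each of two analysis sets, and the narrower pair stands in the section that programmers will treat as governing. Arms A and B exist only in Part 2 (SAP 1.3), so the Section 1.2 wording removes both from every PK and ADA output.

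The main casualty is the part of the secondary objective that concerns daratumumab given alone. Arm A is the only group never exposed to JNJ-63723283. Without it, two sources of daratumumab-alone data remain:

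- the run-in samples from Cycle 1 Day 1, taken before the first JNJ-63723283 dose on Day 2;
- any daratumumab-alone dosing in run-in subjects after JNJ-63723283 was stopped, which follows exposure to it.

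If the footnotes and Section 1.2 were programmed separately, the set counts in TSIPOP01 would also disagree with the N in the PK and ADA tables. If Section 1.2 drove both, the counts would agree but the footnotes would misdescribe them.

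**Working it through.** The plan states no figure to reproduce. The check compares the texts and then counts what would be lost.

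**Which text includes Part 2?**

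| Source | PK | ADA |
|---|---|---|
| SAP 1.2 | Part 1 only | Part 1 only |
| SAP TSIDEM-ST03, footnotes b and c | Run-in or Part 2 | Run-in or Part 2 |
| Protocol 9.3.3 | Run-in, Arm A, Arm B | Not covered |
| Protocol 11.4 (PK), 11.5 (ADA) | No limit by part | No limit by part |
| SAP 3, Layout 3 (PK), Layout 4 (ADA) | Columns not readable in the available text | Only the run-in column is visible |

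Rows 1 and 2 cannot both hold. For PK, row 1 also contradicts row 3. The silence of Protocol 11.4 fits the wider set but does not by itself contradict Section 1.2.

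**Is a reason given?** None was found. Protocol 9.3 stops PK and immunogenicity evaluations in the Daratumumab Monotherapy Period, which does not remove samples already taken in Part 2. Protocol 11.12 limits reporting to a descriptive summary, but of all treated subjects. The SAP amendment history records only the added biomarker section. SAP Section 8 refers to a further document (DPS part 2) that is not available here, so a reason there cannot be excluded.

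**Outputs affected (SAP Section 2).** On the PK-evaluable set: TPKCONC01, TPKCONC02, GPKCONC01, GPKCONC02. On the immunogenicity set: TPKIR01, TPKIR02, LPKCONC01, LPKCONC02. Total 4 + 4 = 8. Under Section 1.2 the number of Part 2 subjects in each is 0, whatever number was treated. LPKCONC01 and LPKCONC02 list only ADA-positive subjects, so they lose an entry only if a Part 2 subject is positive.

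**Samples per Arm A subject (Protocol Table 2, daratumumab columns, through Cycle 3 Day 1).**

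- Concentrations: predose and end of infusion on Day 1 of Cycles 1, 2 and 3, so 2 × 3 = 6. Without the Cycle 1 predose sample, 6 − 1 = 5 are post-dose.
- ADA: predose on the same three days, so 3. Without Cycle 1, 3 − 1 = 2 are post-dose.

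End-of-treatment and later samples are not counted.

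**Range.** The number of treated Arm A subjects is not given (40 were planned). For an assumed number n who reached Cycle 3 Day 1 before sampling stopped:

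| n | Post-dose concentrations lost (5n) | Post-dose ADA samples lost (2n) |
|---|---|---|
| 1 | 5 | 2 |
| 5 | 25 | 10 |
| 10 | 50 | 20 |

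Under footnotes b and c the loss is 0.

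**The case against.** The conflict itself cannot be argued away, but its reach and direction can.

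**Reach.** Arm B may be empty. Layouts 1 and 2 show only Arm A under Phase 2, and the footnote key and the biomarker mock name only Arm A from Part 2. Protocol Table 2 collects JNJ-63723283 samples only in the run-in and Arm B. If nobody in Arm B was treated, the four JNJ-63723283 outputs (TPKCONC02, GPKCONC02, TPKIR02, LPKCONC02) would lose no results, at most a header N. The real loss would fall on the four daratumumab outputs. This is likely but not proven: SAP 1.3 and the listing sort orders still name Arm B. The sample counts above cover only Arm A and daratumumab, so they are unaffected.

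**Direction.** The contrast between the safety set and the next two sets could be deliberate, and footnotes b and c could have carried over the ending of footnote a. The visible part of Layout 4 ("Layout 4: To be used in immunogenicity tables") shows only the run-in. For PK, Protocol 9.3.3 still favours the wider set. For ADA the documents do not settle the intention, so the claim there is limited to the SAP's internal conflict.

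**Weight.** Protocol 9.3.3 was written for the full design. After Amendment 2 the study is closed to enrolment and reporting is descriptive. That lowers the stakes but does not justify dropping Part 2 subjects, because Protocol 11.12 covers everyone who was treated.

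**Conclusion.** The concern holds. Both sets are defined in two incompatible ways within the SAP, and for PK the Section 1.2 version also departs from Protocol 9.3.3 without explanation.

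If Section 1.2 is applied, Part 2 contributes 0 subjects to 8 outputs. Each Arm A subject who reached Cycle 3 Day 1 while sampling continued would lose 5 post-dose daratumumab concentrations and 2 post-dose ADA samples. The totals depend on an assumed number of such subjects, and any loss of JNJ-63723283 results depends on Arm B subjects having been treated.

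No primary endpoint or hypothesis test depends on these outputs. It should still be corrected before the outputs are produced, because scheduled samples that serve a stated secondary objective would otherwise be left out without any stated decision.

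**What to change.** - **PK.** Extend the Section 1.2 definition to cover the run-in or Part 2, matching footnote b and Protocol 9.3.3. Check that Layout 3 carries the Part 2 arm or arms.
- **ADA.** Use one definition in Section 1.2, footnote c and Layout 4. The preferred choice is footnote c's, set per drug: at least one dose of that drug and at least one later sample. TPKIR-ST01 already works this way for daratumumab ("Subjects with appropriate samples had 1 or more samples obtained after their first daratumumab administration"), and the TPKIR02 programming note carries it over to JNJ-63723283. Also reconcile Protocol 11.5, which requires doses of both drugs, with the SAP, which accepts either.
- **If a Part 1-only cut was intended for either set.** Say so in Section 1.2 with the reason, record it for PK as a change from Protocol 9.3.3, and correct footnotes b and c.

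Keep the summaries descriptive. The cost is a few words in Section 1.2 or the footnotes, one line for the ADA set and a check of two layouts. No new data are needed, since Protocol Table 2 already scheduled the Arm A samples.
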